4.8.2 Treatment compliance

Every sixth month, subjects are provided with two boxes of IMP, each containing 100 pills. Subjects are to take one pill per day. Subjects treated with adjuvant chemotherapy, who, for medical reasons, should not receive ASA during said treatment are allowed to start taking the IMP after termination of chemotherapy. Subjects are also allowed to pause taking the IMP for up to 30 days in a row during the trial. All treatment pauses, for any reason, are entered with a start and end date in the eCRF.

At each phone contact and clinic visit, the subject is asked how often they forget to take the IMP, with response options

- Never/Rarely
- Once in a while
- Sometimes
- Often
- Always.

At each clinic visit, the subject brings the IMP packages provided to them at the preceding clinic visit, the remaining pills are counted mechanically and the sum is entered into the eCRF.

Compliance until the last clinic visit (C_{LCV}) will be calculated as

$$C_{LCV}$$
 % = $\frac{DP \text{ before the final clinic visit - RP up to and including the final clinic visit}}{TD until the final clinic visit - number of days on allowed break before the final clinic visit} •100,$

where DP refers to the total number of dispensed pills, RP to the total number of remaining pills, and TD to the total number of potential treatment days. The number of days on break before the final clinic visit only includes breaks that are maximum 30 days or related to adjuvant chemotherapy, i.e. breaks that are allowed by the study protocol.

Subjects with an EoS event before the first clinic visit, in which the first pill count takes place, but after the first phone contact, will not have any pill counts in the eCRF. However, they will have been asked at the first phone contact (Visit 4) how often they forget to take the IMP. Compliance until Visit 4 (C_{V4}) for these subjects will be defined as 80 % if the response is "Never/Rarely" or "Once in a while", and 0 % if the response is "Sometimes", "Often", or "Always". C_{LCV} (or C_{V4}) for subjects with visits outside of the allowed time-window of ± 21 days will be calculated similarly as if their visits had been within the allowed time-window.

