Subjects leaving the trial for any reason between two clinic visits, or between the first phone contact and the succeeding clinic visit, will not have a compliance measurement for the time between the last clinic visit (or Visit 4) and trial exit. For these subjects, an assumption on how long C_{LCV} (or C_{V4}) is assumed valid must be made. Denote the last date for which C_{LCV} (or C_{V4}) is assumed valid $D_{LCV/V4}$. For subjects experiencing recurrence, death, or other cancer, $D_{LCV/V4}$ will be defined as the date of last IMP intake, if such a date is registered in the eCRF, or the event date (see Section 6.2.1 for definition), whichever comes first. For subjects leaving the trial before an endpoint or before trial completion, $D_{LCV/V4}$ will be defined as the date of last IMP intake, if such a date is registered in the eCRF, or the Visit 15 date/EoS date, whichever comes first. For subjects completing 3 years in the trial, $D_{LCV/V4}$ will be defined as the date of Visit 15 (the 3-year follow-up clinic visit). The number of days for which C_{LCV} (or C_{V4}) will be assumed valid will be calculated as days from randomization until $D_{LCV/V4}$, subtracting the number of days on treatment breaks (before $D_{LCV/V4}$) not allowed by the protocol (see above), for each randomized subject having received the IMP at least once.

For subjects reaching a trial endpoint, days from $D_{LCV/V4}$ until the event date will be defined as having 0 % compliance. Similarly, for subjects leaving the trial before completion, days from $D_{LCV/V4}$ until 3 years from randomization will be defined as having 0 % compliance. For all subjects, regardless of trial completion or exit, days on treatment breaks (before $D_{LCV/V4}$) not allowed by the study protocol will be defined as having 0 % compliance. Overall compliance (OC) will be calculated as a weighted average between C_{LCV} (or C_{V4}) and 0, as follows

OC % =
$$\frac{\text{Valid days*C}_{\text{LCV or V4}} + \text{Zero-compliance days*0}}{\text{Valid days+Zero-compliance days}}.$$

Subjects with an EoS event before the first phone contact will not have answered the question on frequency in taking the IMP, or have any pill counts in the eCRF, hence, it is not possible to calculate compliance for such subjects.

See 6.2.2 for derivation of the variables needed for compliance calculation.

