5.2.2 Per protocol populations

The per protocol population at 3 years (PP3) consists of all subjects in the FAP who had at least 80 % compliance, fulfill all eligibility criteria, no significant protocol violations, and have either reached a study endpoint (recurrence, other cancer, or death) within 3 years, or completed at least 3 years in the trial.

The per protocol population at 5 years (PP5) consists of all subjects in the FAP who had at least 80 % compliance, no significant protocol violations, fulfill all eligibility criteria, and have either reached a study endpoint (recurrence, other cancer, or death) within 5 years, or completed at least 5 years in the trial.

Subjects who are thought to fulfil all eligibility criteria at randomization, but later are found not to fulfil all eligibility criteria will be excluded from the PP3 and PP5, for example subjects where Lynch syndrome is discovered after randomization.

Significant protocol violations include more than 12 weeks from surgery until randomization, leaving the study because of pregnancy, lack of compliance with the study protocol, wanting to leave the study, refusal to cooperate, other medical reasons, e.g. initiating another treatment not compatible with ASA, or leaving the trial because of an SAE/AE.

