6.2.2 Variables for compliance calculation

See Section 4.8.2 for the definition of overall compliance.

The number of treatment days until the last clinic visit will be calculated as days from the date of randomization (*A_randomiseringsdatum*) until the date of the last clinic visit (*V_Visitdatum* for the latest clinic visit, where clinic visits are *V_Visit* V5, V6, V7, V8, V9, V10, V11, V13, V15).

The number of dispensed pills at a certain clinic visit will be calculated as 100 times the number of unique package numbers (*S_Package_Number*) for packages that are not shredded (*R2465T32612_MAKULERAD*) or not found at the clinic (*S_Not_Found*).

The total number of dispensed pills will be calculated as the sum of the dispensed pills at each visit.

The total number of remaining pills will be calculated as the sum of the number of remaining pills for each clinic visit (S_returned_number). If the package was lost by the subject (S_Lost_Drug="True"), and S_returned_number equals 0 or "NA", the number of remaining pills for that package will be defined as 100, to not overestimate compliance.

The number of days on break will be calculated as the sum of days from $V_UppehallFromDatum$ until $V_UppehallTomDatum$, for all visits where $V_Uppehall=1$. Treatment breaks that are longer than 30 days and unrelated to adjuvant chemotherapy will be defined as non-compliant with the study protocol. Similarly, breaks that are at most 30 days of related to chemotherapy will be defined as compliant with the study protocol. Days on treatment break that are overlapping with a later registered treatment break will be subtracted.

Compliance for subjects with an EoS event after the first phone contact but before the first clinic visit will be based on the variable *V_LMIntag* for *V_Visit*=V4.

The date for which C_{LCV} (or C_{V4}) is considered valid until ($D_{LCV/V4}$) is $E_sistaintag$, dfs_event_date , $E_endofstudydtm$, or $v15_visitdatum$. The number of valid days will be calculated as the number of days from randomization ($A_randomiseringsdatum$) until $D_{LCV/V4}$, subtracting the number of days on non-allowed treatment break (see above). The number of zero-compliance days will be calculated as days from $D_{LCV/V4}$ until $E_endofstudydtm$ or 3 years from randomization, adding the number of days on non-allowed treatment break.

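### An allowed treatment break still open when an event occurs is scored as non-compliance, so membership of the exploratory per-protocol sets can depend on the event itself

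*SAP*

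**What the plan says.** **Threshold.** SAP 5.2.2 defines PP3 as "all subjects in the FAP who had at least 80 % compliance, fulfill all eligibility criteria" and without significant protocol violations, who "have either reached a study endpoint (recurrence, other cancer, or death) within 3 years, or completed at least 3 years in the trial". PP5 has the same 80 % threshold. Subjects with events are therefore kept or dropped on their compliance score.

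**Allowed breaks.** In the pill-count measure up to the last clinic visit (C_LCV), SAP 4.8.2 removes break days from the denominator. That deduction "only includes breaks that are maximum 30 days or related to adjuvant chemotherapy". SAP 6.2.2 says the same breaks "will be defined as compliant with the study protocol". Protocol 10.7.8 caps pauses for procedures needing low molecular weight heparin at 30 days. It gives no day limit for a pause caused by a platelet drop under chemotherapy.

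**Extension to the event.** SAP 4.8.2 sets a date D up to which the measured compliance is taken as valid.

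- Subjects with recurrence, death or other cancer: D is the registered date of last IMP intake or the event date, whichever is earlier. Days from D "until the event date will be defined as having 0 % compliance".
- Subjects completing 3 years: D is Visit 15, and the last-intake date is not used.
- All subjects: among breaks before D, only those not allowed by the protocol count as zero.

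**The concern.** A subject who is on an allowed break when the event occurs took the last tablet before the break began. D moves back to that tablet, and the whole open break falls into the zero-compliance period. If the subject had restarted the day before the event, the same break would lie before D and count as valid. For a completer it would also count as valid.

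Only an event (or an early exit) moves D back, so the outcome decides how protocol-allowed behaviour is scored. A per-protocol set should not be selected in this way. The subjects exposed are those paused for chemotherapy or a procedure. The stabilized weights in SAP 8.3 do not repair it: they model the treatment received from baseline covariates, and adjuvant chemotherapy is not among them.

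**Working it through.** The plan states no figure for this point, so there is none to reproduce.

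**Formula (SAP 4.8.2).** OC = C × valid days / (valid days + zero-compliance days). For an event on day T, an allowed break of b days still open, a registered last-intake date and no other zero days: valid = T − b and zero = b, so OC = C × (T − b)/T. This is below 80 % when T < b/(1 − 80/C), with C in per cent.

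**Step 1: one subject, both rules.** Last tablet on day 30, chemotherapy-related break open from then, Visit 5 on day 182, recurrence on day 200. C_LCV = 30/(182 − 152) = 100 %, because the 152 break days are deducted as allowed. Then OC = 100 × 30/200 = 15 %, because the same days, and those up to the event, return as zero-compliance days. Not counting them as zero gives OC = 100 %.

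**Step 2: which compliance value applies when.**

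- Before Visit 4 (month 3): SAP 4.8.2 says compliance cannot be calculated, with or without a break.
- Visit 4 to first clinic visit: C_V4 is 80 % or 0 %, so a single zero day excludes. With 119 valid days and 1 zero day, 80 × 119/120 = 79.3 %. A 30-day break open at day 120 gives 80 × 90/120 = 60 %.
- From Visit 5: C_LCV applies. At the earliest Visit 5 (about day 182 − 21 = 161), a 30-day open break at C_LCV 100 % gives 131/161 = 81 %, so the subject stays in.

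**Step 3: thresholds after Visit 5.** Events before the day shown are excluded. Break lengths above 30 days are assumptions; the documents give no chemotherapy duration.

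| Open break | C_LCV 100 % | 95 % | 90 % | 85 % |
|---|---|---|---|---|
| 30 days | none (Step 2) | 190 | 270 | 510 |
| 60 days | 300 | 380 | 540 | 1020 |
| 90 days | 450 | 570 | 810 | beyond 3 years |
| 180 days | 900 | beyond 3 years | beyond 3 years | beyond 3 years |

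**Step 4: rough count in the C_V4 window.** Inputs: 18 % placebo recurrence at 3 years, RR 0.38 (so 6.84 % on ASA) and 150 per arm, all from SAP 4.5.2. Constant hazards are assumed.

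- Months 0-6: 150 × (1 − 0.82^(1/6)) + 150 × (1 − 0.9316^(1/6)) = 6.6 events.
- Months 0-3: 150 × (1 − 0.82^(1/12)) + 150 × (1 − 0.9316^(1/12)) = 3.3 events, before Visit 4 and not calculable anyway.
- Months 3-6: 6.6 − 3.3 = 3.3 events exposed.
- If 30-60 % receive chemotherapy and 10-50 % of those are paused at the event (both assumed): 3.3 × 0.3 × 0.1 = 0.1 to 3.3 × 0.6 × 0.5 = 1.0 events. The design total is 150 × 0.18 + 150 × 0.0684 = 37.3.

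**Step 5: end date.** SAP 4.8.2 ends the zero-compliance days at the event date for subjects with an endpoint. SAP 6.2.2 ends them at E_endofstudydtm or 3 years from randomization. The two sections do not define the same variable.

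**The case against.** The best defence is that a subject with 15 % of days on drug does not belong in a per-protocol set, whatever the reason. That would be a coherent rule, but it is not the SAP's: an equally long chemotherapy break that ended just before the event counts as valid.

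Other parts of the defence stand. The rule needs a registered last-intake date; without one, D is the event date and the break is valid. In the C_V4 window any gap before the event excludes, so breaks are not singled out there. The analyses affected are optional, report no p-values, and SAP 8.3 already requires their limitations to be highlighted. The primary endpoint and secondary endpoints 1-5 use the FAP.

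A reader might infer more than the documents support:

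- *A 30-day heparin pause drops every otherwise compliant event before day 150.* The formula gives 150 at C = 100 %, but no pill count exists that early. Step 2 shows what happens instead.
- *All early recurrences are exposed.* About half of those expected in months 0-6 precede Visit 4.
- *A completer with the same long break shows the size of the bias.* A 153-day break scored as zero over 1,096 days still leaves 943/1,096 = 86 %, so the completer passes under either rule. The fair contrast is with an event subject whose break had ended.
- *Starts delayed by chemotherapy always give a 0/0 score.* This needs the delay to be entered as a break from randomization, and the SAP does not say how it is coded.
- *The hazard ratio is biased in a known direction.* Nothing shows that exclusions differ by arm; the trial is double-blind and populations are assigned before unblinding.

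**Conclusion.** Wrong as written, and minor. SAP 4.8.2 penalises an allowed break only when it is still open at the event, against its own definition and that of 6.2.2. Membership of PP3 and PP5 can therefore turn on whether an event interrupted the break.

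The reach is certain only for events between Visit 4 and the first clinic visit. Later it depends on break length and on C_LCV: heparin pauses matter only when C_LCV is below 100 %, while chemotherapy breaks can reach well into the second year or beyond. The number of subjects cannot be derived from the documents. The 0.1 to 1 event in months 3-6 rests on assumed chemotherapy and pause rates, constant hazards, the design rates for the exon 9/20 group and a registered last-intake date. Some later events in long chemotherapy breaks would add to it. The direction of any effect on the per-protocol hazard ratio is unknown.

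**What to change.** Amend SAP 4.8.2 and 6.2.2 before the blind is broken:

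1. State that allowed-break days between D and the event date are not zero-compliance days, and that an open break is closed at the event date when it is classified.
2. Use one end date for zero-compliance days in both sections.
3. Class subjects with no IMP-due days before the event, or with a zero denominator in C_LCV, as not calculable, as 4.8.2 already does for events before Visit 4. Report their number by arm. Without this rule, removing break days could leave some subjects with an undefined score.

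The cost is a few sentences and a few lines of code. Break start and end dates are already in the eCRF. The change concerns scoring only and leaves the conduct of treatment untouched.

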4.8 Trial assessments

Written informed consent is given by the patient in the first screening visit, which takes place before or shortly after surgery (allowing for randomization to be performed within 12 weeks from surgery).

In the second screening visit, which takes place after surgery, inclusion and exclusion criteria are assessed in patients with tumors harboring somatic alterations in the PIK3CA, PIK3R1 or PTEN genes. Patients without such somatic alterations, and patients not fulfilling all inclusion criteria, or fulfilling at least one exclusion criteria are excluded from the trial. However, patients with regular use of ASA (>3 doses/week) fulfilling all other eligibility criteria, are included in an observational arm.

Randomization takes place in the third visit, in which the subject is also provided with IMP for 200 days. The treatment period begins at the randomization visit and ends after 3 years.

A phone contact is made with the subject three months from randomization, and thereafter every sixth month. Also, subjects visit their respective site every sixth month from randomization, i.e,. the subjects are in contact with the site every third months for three years. At the end of the follow-up period, five years from randomization, there is an additional visit or phone contact for subjects who have completed three years in the trial (up to and including Visit 15). The trial assessments, starting from randomization, are visualized in Figure 2, and described in detail in Table 4.

[figure not shown]

Figure 2. Time-line of trial assessments. The dice icon refers to Randomization, the phone icon to Phone contact, the human icon to Clinic visit, and the skeleton icon to clinic visit including examination with CT/MRI.

Table 4. Overview of trial assessments

Assessment/Visit	Random- ization (R)	First phone call	First site visit	Subsequent phone calls	Subsequent site visits	Final visit/phone call
Visit no.*	3	4	5	6, 8, 10, 12, 14	5, 7, 9, 11, 13, 15	16
Timepoint	0	3mo after R	6mo after R	Every 6mo after first phone call	Every 6mo after first site visit	5y from R
Visit/call window	-	±21 days	±21 days	±21 days	±21 days	±30 days
Provide with IMP	Yes		Yes		Yes	
Assess AEs		Yes	Yes	Yes	Yes	
Subject asked about compliance		Yes	Yes	Yes	Yes	
Remaining pill count			Yes		Yes	
Record concomitant medication		Yes	Yes	Yes	Yes	
CT/MRI of thorax and abdomen					Yes (visit 7 and 15 – 1y and 3y after R)**	

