Measure carcinoembryonic antigen (CEA)					Optional, visit 7 and 15 – 1y and 3y after R	Optional
Subject asked about regular use of ASA after end of trial intervention						Yes
CRC recurrence/Death (and corresponding dates)						Yes

^{*}Visits 1 and 2 are screening visits.

Subjects leave the IMP part of the trial at Visit 15, or at fulfillment of an end of study (EoS) reason. EoS reasons are

- Death,
- CRC recurrence,
- Severe unexpected AE,
- Pregnancy,

^{**}Two Finnish sites do not include CT/MRI of thorax and abdomen as part of their standard of care.

- Other medical reason (including other cancer),
- · Wanting to leave the study,
- · Lack of compliance with study protocol,
- Refusal to cooperate,
- Other reason (specified in the eCRF by study personnel).

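### Read literally, the 80% compliance rule keeps subjects whose recurrence, other cancer or death precedes Visit 4 out of PP3 and PP5, because the SAP gives them no compliance value

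*SAP*

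**What the plan says.** SAP 5.2.2 builds PP3 from "all subjects in the FAP who had at least 80 % compliance", who also meet the eligibility criteria, have no significant protocol violation, and "have either reached a study endpoint (recurrence, other cancer, or death) within 3 years" or completed three years. PP5 has the same structure at five years. All these conditions must hold together. Reaching an endpoint meets the follow-up condition but does not waive the compliance condition.

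SAP 4.8.2 derives compliance from pill counts at clinic visits. For an EoS event between the first phone contact and the first clinic visit there is no pill count, but "they will have been asked at the first phone contact (Visit 4) how often they forget to take the IMP". A good answer is scored by convention: compliance "for these subjects will be defined as 80 % if the response is" one of the two best categories, and 0% otherwise. For an EoS event before that contact there is neither a count nor an answer, and the section concludes: "hence, it is not possible to calculate compliance for such subjects".

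On timing, SAP 4.8 states: "A phone contact is made with the subject three months from randomization". Table 4 allows ±21 days. On EoS: "Subjects leave the IMP part of the trial at Visit 15, or at fulfillment of an end of study (EoS) reason". The reasons listed there include death and recurrence, and other cancer under other medical reasons. SAP 6.2.2 adds no rule for the earliest cases: "Compliance for subjects with an EoS event after the first phone contact but before the first clinic visit will be based on" the Visit 4 answer, and nothing is given for EoS before Visit 4.

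**The concern.** For a subject who reaches an endpoint very early, entry to the per-protocol set is decided by when the event happened, not by how the tablets were taken. A subject with identical intake and no event reaches Visit 4, is scored, and keeps the first three months of event-free time in the analysis. That is selection on the outcome.

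It also works against the SAP's own design. Unlike the definition in Protocol 10.13.6, which asks for three completed years, SAP 5.2.2 admits subjects with an endpoint. The stabilised weights in SAP 8.3 do not repair the loss: they model the treatment received from baseline covariates, not inclusion in the set. The reasons given there for not using censoring weights do not mention missing early compliance. At stake is whether a difference between the PP and FAP results could be read as an adherence effect when part of it comes from the population definition.

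**Working it through.** **1. The rules side by side.**
- Early recurrence, death or other cancer is an EoS reason (SAP 4.8).
- EoS before Visit 4 means no compliance value (SAP 4.8.2), and no derivation is given (SAP 6.2.2).
- PP3 and PP5 require at least 80% (SAP 5.2.2).
- No section says how a missing value is classified.

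Taken literally, such a subject does not satisfy the 80% condition. Subjects who leave before Visit 4 without an endpoint generally fail PP3 and PP5 on follow-up anyway, so the issue concerns endpoint cases.

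**2. Inputs for the size (SAP 4.5.2).** Placebo 3-year recurrence 18%; RR 0.38, so ASA 0.18 × 0.38 = 6.84%; two-sided alpha 0.05; power 80%; 135 per arm, or 150 with 10% drop-out.

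**3. The plan's own figure.** Two-proportion test with pooled variance, mean risk 0.1242:
n = [1.96·√(2 × 0.1242 × 0.8758) + 0.8416·√(0.18 × 0.82 + 0.0684 × 0.9316)]² / 0.1116² ≈ 136, against 135 stated. Also 135/0.90 = 150. The figures reproduce.

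**4. Recurrences before Visit 4.** Assuming constant hazards, the expected number by day t is 150 × [1 − (1 − p)^(t/1095.75)]. The 3-year total is 150 × (0.18 + 0.0684) = 37.3.

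| Visit 4 at | Placebo | ASA | Total | Share of 37.3 |
|---|---|---|---|---|
| day 70 | 1.89 | 0.68 | 2.57 | 6.9% |
| day 91.3 | 2.46 | 0.88 | 3.34 | 9.0% |
| day 112 | 3.01 | 1.08 | 4.09 | 11.0% |

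Deaths and other cancers before Visit 4 are additional; the documents give no rate for them.

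**5. Effect on recurrence risk in PP3** (Visit 4 at month 3, no other exclusions):
- Placebo: (27.00 − 2.46)/(150 − 2.46) = 16.6% instead of 18.0%.
- ASA: (10.26 − 0.88)/(150 − 0.88) = 6.3% instead of 6.84%.

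**6. Effect on the hazard ratio.** The implied constant HR is ln(0.9316)/ln(0.82) = 0.357. Unstratified Cox models were fitted to 3000 simulated trials of 135 per arm, with and without the subjects who had an event before month 3 (medians):

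| Scenario | HR, all events | HR, early events dropped | SE of log HR |
|---|---|---|---|
| Proportional hazards | 0.358 | 0.357 | 0.391, then 0.411 |
| No ASA effect for 3 months (assumed) | 0.406 | 0.348 | 0.372, then 0.412 |

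Analytic check of the lag case, as a ratio of cumulative hazards: (0.25 × 1 + 2.75 × 0.357)/3 = 0.41 with all events, and 0.357 after month 3. The shift on the log scale is ln(0.41/0.357) = 0.14 (0.15 in the simulation), a little over a third of the standard error.

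**The case against.** The strongest reply is that SAP 5.2.2 never states this exclusion. It leaves a missing compliance value unclassified, and SAP 5.2 has population status assigned before the blind is broken, so any ruling would be made without knowledge of arm. This stands as far as the wording goes: the exclusion is the literal consequence of two rules, not a written sentence. It does not remove the problem. Blinding to arm does not prevent selection on event timing, and a programmer applying the text would drop these subjects.

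A reader might infer that PP3 contains no event from the first three months. It does not follow. The cut-off is each subject's actual Visit 4, which may fall near day 70, so an event at day 80 after a day-70 call can be scored.

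A reader might also infer that the variables in SAP 6.2.2 suffice to compute compliance for these subjects. They do not. Last-intake date (used only if registered), breaks and event date give days at risk of intake; the missing item is the fraction of tablets taken. Scoring those days as fully compliant would also clash with the 80% convention for Visit 4 responders, and with the rule in SAP 6.2.2 that counts lost packages as unused so as not to inflate compliance.

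A third tempting reading is that the PP hazard ratio is biased toward ASA. Under proportional hazards there is practically no shift, and the documents specify no lag. SAP Table 10 separately plans a FAP analysis of TTR starting six months from randomization, which addresses early events in a labelled way.

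Finally, the stakes are low. The PP analyses are optional, exploratory and reported without p-values, and SAP 8.3 requires their limitations to be highlighted. That is correct, although the reasons it lists do not include this one.

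**Conclusion.** The concern holds as a minor one. Applied as written, SAP 4.8.2 and 5.2.2 together keep subjects out of PP3 and PP5 because their endpoint came before their own Visit 4, while the matching event-free time of other subjects stays in.

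The size is about 3 of 37 expected Mutation A recurrences at 150 per arm. This rests on the plan's 18% and RR 0.38 and on an assumed constant hazard. It is probably an upper estimate, because planned CT/MRI is at years 1 and 3 and few recurrences may be detected sooner. Recurrence risk in PP3 is slightly understated in both arms. The hazard ratio moves toward ASA only under a delayed effect: about 0.41 to 0.35–0.36 for an assumed 3-month lag.

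The documents do not support extending the point to the main results: the primary analysis and secondary endpoints 1–5 use the FAP (SAP Table 9).

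**What to change.** Before the blind is broken, add to SAP 4.8.2 and 5.2.2 that a subject with an endpoint before Visit 4 is not excluded from PP3 or PP5 solely because compliance cannot be calculated. Retain the subject if IMP was received, no non-allowed break or stop of IMP before the event is recorded, and the other conditions of 5.2.2 are met.

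Treat such a subject as meeting the threshold; do not assign 100%. This matches what the 80% convention already demands of Visit 4 responders, for whom a single zero-compliance day fails the threshold (80 × 120/121 = 79.3%).

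Report the number of these subjects by arm, and give PP3 and PP5 results with and without them.

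The cost is a few lines of SAP text and code using data already collected. The downside is that intake for these few subjects is assumed, not measured, so someone who took no further tablets but has no recorded stop could be included. The paired results show how much depends on that assumption.
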